**Abstract:**

The HEAL Diabetes Program is a multicomponent intensive plant-forward healthy eating program designed to reverse diabetes. Several recent studies, most notably the Diabetes UK-funded Diabetes Remission Clinical Trial (DiRECT) in England and Scotland, have demonstrated that intensive programs for weight loss and weight loss maintenance can lead to long-term remission of diabetes for as many as half of patients with early Type 2 (adult-onset) diabetes. Furthermore, the U.S. Preventive Services Task Force has recommended that *all patients* with obesity and at highest risk for diabetes be referred to such intensive multicomponent behavioral weight loss interventions, but no such programs are available for people living in the low-income and underserved areas of Memphis. This effort will pilot an innovative, culturally tailored, and intensive healthy eating program designed to reverse diabetes based in the UTHSC Neighborhood Health Hub located in low-income neighborhoods to demonstrate that this approach will work in Memphis to improve and extend people's lives. The HEAL Diabetes Pilot Program will: a) engage and retain a minimum of 30 patients with Type 2 diabetes and obesity to participate in the program as well as 30 additional "control" patients who will receive routine care, and b) assess patient outcomes including weight loss and rates of diabetes remission using average blood sugar (hemoglobin A1c) over a six-month period.

**BACKGROUND AND SIGNIFICANCE****A. Significance.**

**A1. Type 2 diabetes is epidemic among the medically underserved.** The growing worldwide epidemic of Type 2 diabetes (T2D) and other obesity-associated chronic conditions (OCC) disproportionately affects minority and medically underserved subpopulations, impacting over 10 million people residing in medically underserved areas in the U.S. Researchers have long known that weight gain and obesity are the main drivers of T2D, but little progress has been made addressing obesity in primary and specialty care settings. Low income and African American patients are less likely to get recommended care for T2D and other OCC, and as a result are much more likely to experience diabetes-related amputations, kidney failure, and premature death. Yet despite low-income and minority populations facing special barriers to effective T2D self-care related to food insecurity and other social determinants of health (SDOH), most T2D behavioral interventions are tailored for the majority, higher-income, patient populations. Thus, low-income and minority groups need specific culturally-tailored solutions that address any particular SDOH they face. Life expectancy is markedly reduced in patients with T2D, largely through the impact of the multiple OCC that commonly accompany T2D, including cardiovascular disease, cancer, and chronic kidney disease. Intensive medication therapy to lower blood sugar, cholesterol, and blood pressure in patients with T2D has led to modest improvements in real-world major clinical outcomes at best, in part because of the challenges of adherence to multiple medications particularly among vulnerable and medically underserved populations. Although weight management is considered essential therapy for people with T2D and other obesity-associated chronic conditions, lack of pragmatic approaches for implementing effective weight loss programs for this population has served as a critical barrier to achieving better outcomes for vulnerable patients with T2D.

**A2. Evidence on best diet composition supporting food as medicine hypothesis.** Numerous studies have thus far clearly established the benefits of plant-forward diets (i.e. diets emphasizing plant-based foods). Large observational studies have demonstrated substantial survival benefits for a plant-forward Mediterranean diet related to cardiovascular disease and multiple other chronic conditions. A large randomized controlled trial (N=322) confirmed that both Mediterranean and low-carbohydrate diets have similar sustained impacts on weight and cardiometabolic health. Studies of pre-diabetes and diabetes remission support a relatively high-protein diet (26-30% protein vs. 15%) for effective and sustained weight loss while maintaining lean body mass. New evidence from an inpatient randomized controlled trial of ad libitum food intake shows that ultra-processed diets cause excess calorie intake and weight gain, providing evidence that processed foods are primary vectors of obesity that must be eliminated from diets to achieve and sustain weight loss.

**A3. New powerful evidence demonstrating effectiveness of primary care-based multicomponent interventions for rapid weight loss, weight loss maintenance, and diabetes remission.** The Diabetes Remission Clinical Trial (DiRECT), an open-label, cluster-randomized pragmatic trial in 49 primary care practices in low-income areas of Scotland and England, recently demonstrated that such interventions can achieve and sustain similar results to bariatric surgery. DiRECT used health coaching by nutritionists in primary care practices, intensive preparation for change, total diet replacement (TDR), and physician-supervised medication discontinuation (PSMD), to achieve an average weight loss of 10.0 kg, diabetes remission in 46% of those in the treatment group at 1 year, sustained remission in 36% at 2 years, and substantial improvements in other biological health outcomes, at low cost. Best evidence from DiRECT and other studies suggests that these intervention components have the most potential to achieve similar outcomes in at-risk populations.

**A4. Intensive multicomponent behavioral weight loss interventions most effective.** The U.S. Preventive Services Task Force (USPSTF) concluded that adults with obesity benefit most from behavioral weight loss interventions that are intensive and multicomponent. A systematic review of the Community Preventive Services Task Force found sufficient evidence to particularly recommend technology-supported multicomponent coaching or counseling interventions to help adults achieve and maintain weight loss. Pragmatic trials of these multicomponent interventions in obesity-associated T2D are desperately needed. The USPSTF has called for well-designed pragmatic comparative effectiveness trials to test and disseminate multicomponent interventions in primary care settings and to provide evidence regarding most effective intervention components. The USPSTF has identified subpopulations such as high-risk racial and ethnic groups as important targets for further outcomes research. Communities that are predominantly African American, low-income, and in medically underserved areas of the South are among those in greatest need. Over 40% of African American men and over 50% of African American women suffer from obesity. Diabetes prevalence exceeds 18%. Most patients with obesity-associated diabetes also experience additional OCC such as hypertension, hyperlipidemia, and arthritis that contribute to adverse outcomes.

The USPSTF and other critical appraisals of the literature have identified the following component interventions as the most evidence-based and promising for achieving substantial weight loss and diabetes remission in medically underserved populations.

**A4a. Motivational Interviewing-based Health Coaching (MI-based HC).** Motivational interviewing (MI) has demonstrated efficacy and effectiveness across a range of behavior change outcomes. Meta-analyses confirm that MI is more effective than traditional diabetes education and weight management programs in achieving weight loss. Health coaching by non-clinical staff has been identified as among the lowest cost strategies for expanding primary care capacity to support diabetes self-care, with strong evidence of effectiveness from numerous clinical trials. Moreover, recent systematic reviews have identified health coaching as among the most efficacious strategies for engaging patients in behavior change to help adults achieve and maintain weight loss, and improve diabetes outcomes in disadvantaged populations.

**A4b. Tailored Motivational Text Messaging (TM).** TM has been observed to be an effective, low cost approach for engaging patients in diabetes self-care. Numerous studies employing TM have demonstrated improved glycemic control, healthy eating, and physical activity in patients with T2D. Our prior research and those of others have also demonstrated that patients with diabetes are appreciative of TM from their doctor's office. Further, systematic reviews have identified TM as among the most efficacious and low-cost strategies for engaging patients in behavior change and have highlighted the importance of such technology-supported interventions to help adults achieve and maintain weight loss.

**A4c. Total Diet Replacement.** Numerous studies have demonstrated the efficacy of TDR for supporting major changes in eating habits and weight loss for patients with obesity and T2D, and TDR was a core intervention for the DiRECT study. Although some of these studies used liquid meal replacements for initial weight loss, several others have used whole foods throughout. Diet replacement with low glycemic whole food diets is associated with increased satiety and weight loss. TDR requires complete substitution of the individual's habitual diet, giving a period of about 12 weeks to plan a new normal diet for life. Numerous recent studies have also demonstrated effectiveness for healthful food pharmacies, food banks, and food delivery in changing key obesity-related eating behaviors and addressing food access issues for low-income populations.

**A4d. Support Groups.** Although conclusive evidence cannot be drawn regarding the relative effectiveness of group- vs. individual-based interventions, group counseling has served as a fundamental component of most successful multicomponent healthy eating, physical activity, and weight loss interventions. Most notable among these are Look AHEAD (Action for Health in Diabetes), the Activity Counseling Trial (ACT), and

the Diabetes Prevention Program (DPP). Consistent with the Social Cognitive Theory that undergirds the proposed study, evidence suggests that the most successful group counseling programs employ peer social support. Recent systematic reviews have identified peer support groups as a promising strategy that can mitigate the effects of SDOH, and improve T2D outcomes for African Americans and the general population.

**A4e. Cooking Classes.** Many successful multicomponent healthy eating and weight loss interventions such as the DPP have employed cooking classes, and culinary medicine is emerging as a popular intervention among patients and providers. Hands-on cooking classes can improve nutrient intake in people with obesity-associated T2D from diverse ethnic and socioeconomic backgrounds. Further, cooking classes encourage home cooking and increase “food literacy” and self-efficacy or confidence in both basic technical culinary skills and competency to plan, choose, prepare, and consume nutritious food. Consumption of meals at home has been associated with a decreased risk for T2D and less weight gain over time.

**A4f. Physician-Supervised Medication Discontinuation (PSMD).** Numerous studies have highlighted the importance of PSMD for T2D and hypertension patients participating in intensive weight loss to avoid serious hypoglycemia and/or hypotension. Most notably, PSMD was a core intervention for DiRECT.

**A5. Scientific Foundation.** Our objective is to assess the effectiveness of a pragmatic intensive multicomponent weight loss intervention that leverages existing staff and resources in primary care settings with potential to achieve simultaneous improvements in multiple chronic conditions associated with obesity. The **Healthy Eating and Active Living to treat Diabetes (HEAL Diabetes)** pilot study seeks to reproduce the results of the DiRECT study using a similar multicomponent intervention culturally tailored for a U.S. medically underserved population. Data from surgical weight loss trials have shown that bariatric surgery can lead to simultaneous improvements in multiple metabolic parameters and chronic disease states, resulting in frequent diabetes remission and improved health outcomes. Yet, until the recent DiRECT study, little progress had been made in identifying practical behavioral weight loss approaches with similar outcomes. Now, multiple lines of recent evidence reviewed above are converging to demonstrate the component interventions most likely to succeed in achieving the substantial and sustained weight loss necessary to improve T2D outcomes. Based on small studies challenged to deliver culturally appropriate behavioral interventions, many researchers suggest that substantial weight loss and T2D remission are not obtainable or sustainable in low-income and minority populations. The current study seeks to clearly demonstrate that this presumption is wrong.

**A6. Summary.** Although it is premature to conclude that the above intervention components are definitively the most efficacious, our review indicates they are among the most important for multicomponent interventions emphasizing whole foods. This demonstration project will use the above key evidence-based, community-engaged, and culturally-tailored components in a “full-court press” clinic-based intervention based on the Chronic Care Model to substantially impact major biological, metabolic, and patient-reported outcomes. The HEAL Diabetes study will test a primary and specialty care delivered multicomponent healthy eating and weight loss program designed to address and ameliorate the SDOH root causes of the T2D epidemic.

## **B. Innovation.**

The current study is innovative because it has potential to reframe the culture and paradigm of T2D treatment by demonstrating an effective, low-cost, and sustainable multicomponent behavioral intervention in real-world clinical settings. The literature has been biased through comparisons of high-cost surgical interventions with nutritional interventions too under-resourced to achieve similar efficacy. This research will allow us to identify and refine a behavioral treatment protocol that can reverse T2D in routine clinical practice. Further, the proposed study’s focus on improvements in self-efficacy as a fundamental mechanism of action is innovative. Our approach draws on the strong evidence for effectiveness of motivational interviewing in multiple disease states and all its component interventions are designed to enhance patient self-efficacy for healthy eating, physical activity, and weight loss. The proposed study’s selection and cultural tailoring of international best practices in T2D behavioral interventions for maximal impact based on extensive input from patients in a medically underserved U.S. population is also highly innovative. Our study seeks to reproduce the results of the United Kingdom DiRECT study by adapting its interventions in a culturally appropriate and sustainable way for a predominantly African American population in the U.S. As Gamburzew *et al.* note, developing multicomponent interventions that offer understandable nutritional guidance to medically underserved patients in real-world settings, requires specific targeting of ethnic minority populations.

## **C. Approach**

**C1. Study Overview -Overall Goal, Aims, Design.** The proposed pilot study replicates the inclusion criteria and outcome measures of the DiRECT study and tests a multicomponent intervention similar to DiRECT's that is culturally tailored and informed by the preliminary results of our own Management of Diabetes in Everyday Life (MODEL) study. The design is a randomized controlled pilot study in a sample of 72 patients with obesity-associated T2D. Eligible patients will be enrolled and randomized to one of the following two arms: 1) Multicomponent intervention (treatment) group (n=36), or 2) Usual Care (control) group (n=36) as detailed in **Table 1** below.

**C1a. Study Overview.** Research demonstrates that diabetes remission is achievable through weight loss, but pragmatic approaches that leverage existing staff and resources in the healthcare setting to deliver intensive behavioral lifestyle modification interventions are underdeveloped and underutilized. Our goal is to assess the effectiveness of an intensive multi-component plant-forward healthy eating intervention for patients with obesity-associated T2D. Our approach builds on the results of the Diabetes Remission Clinical Trial (DiRECT) study, and the preliminary results of the Management of Diabetes in Everyday Life (MODEL) study, to test a culturally tailored multicomponent intervention designed for a U.S. medically underserved population. This research design is an individually randomized controlled trial in 72 patients with obesity-associated T2D. The Healthy Eating and Active Living to Treat Diabetes (HEAL Diabetes) Study will assess a “full-court press,” clinic-based intervention with these evidence-based components: 1) **Intensive preparation for change** to a plant-forward healthy eating program for weight loss, 2) **Motivational interviewing-based health coaching (MI-based HC)** support for healthy eating and physical activity, 3) **Tailored motivational text messaging** from the health coach, 4) **Total diet replacement (TDR)** with healthy food boxes for 3 months, 5) **Health coach-led support groups**, 6) **Cooking classes**, and 7) **Physician-supervised medication discontinuation (PSMD)**. All components will be individually and culturally tailored to address social determinants of health serving as key barriers to healthy eating and physical activity. The U.S. Preventive Services Task Force concluded that adults with obesity benefit most from behavioral weight loss interventions that are intensive and multicomponent. MI-based HC has been demonstrated to be among the most effective component interventions for weight loss. Our team has extensive expertise implementing these interventions in the settings where low-income individuals with T2D and other obesity-associated chronic conditions receive routine care through the DiRECT, our MODEL, SafeMed, and other studies. DiRECT used health coaching in primary care practices, intensive preparation for change, TDR, and PSMD to achieve an average weight loss of 10.0 kg, diabetes remission in 46% at 1 year, sustained remission in 36% at 2 years, and improvements in key biological health outcomes at low cost. Best evidence suggests that these are among the components with the most potential to achieve similar outcomes in other at-risk populations. Preliminary results from the MODEL study indicate that primary care-integrated MI-based HC is well received, with highest self-reported levels of improvements in health behaviors, confidence, and health outcomes in the MI-based HC group, and overall retention of over 90% in 672 program participants. By directly supporting patients in achieving their health goals, MI-based HC is more effective at engaging patients in self-care than traditional diabetes education or weight loss classes. Furthermore, health coaches integrated into practices are increasingly sustainable due to the growth of value-based payment initiatives.

**C1b. Specific Aims.** In light of the recent evidence indicating that multicomponent behavioral interventions can achieve levels of weight loss and diabetes remission comparable to bariatric surgery, we seek to assess the effectiveness of the most evidence-based of these component interventions delivered in combination.

**Aim 1:** Provide preliminary demonstration of the feasibility, effectiveness, and operational and financial sustainability of a health coach-supported intensive weight loss and weight maintenance program designed for people in Memphis. Specifically, we will:

- A. Assess our recruitment capability and resulting sample characteristics
- B. Evaluate resources and ability to manage and implement the study and study interventions
- C. Evaluate acceptability and suitability of intervention and study procedures (e.g. operational sustainability assessed through participant 3-, 6-, and 12-month program retention and attendance rates)
- D. Preliminary evaluation of participant responses to intervention (see Aim 2 below)
- E. Assess cost effectiveness of the multicomponent intervention (financial sustainability).

**Aim 2:** Quantify and compare the treatment and control groups on the following measures:

A. Primary **biological outcomes** of body weight, blood pressure (number of prescribed blood pressure medications), average blood sugar (hemoglobin A1c [A1c]), and diabetes remission (A1c  $^3 < 6.5\%$ ) after at least 2 months off all diabetes medications except for GLP-1 agonist and/or SGLT-2 inhibitor medications which patients will be allowed to continue or start if desired by patient and recommended by their physician.

B. Secondary **patient-reported outcomes** of self-efficacy and self-care activities related to general diet and exercise.

**C1c. Goal.** The HEAL Diabetes study addresses a critical need to identify effective, scalable, and sustainable behavioral weight-loss approaches to help medically underserved patients in the U.S. achieve substantial weight loss and diabetes remission. We will compare primary biological outcomes (body weight, number of prescribed blood pressure medications, A1c, and diabetes remission), secondary metabolic outcomes (fasting glucose, insulin, insulin resistance, lipid profile, and CRP levels), and secondary patient-reported outcomes (self-efficacy, self-care activities related to general diet and exercise, health-related quality of life, and average pain rating) at baseline and 12-months. Based on DiRECT and MODEL study experience and evidence from other key studies and systematic reviews, we hypothesize that the HEAL Diabetes intervention will result in weight loss  $\geq 10$  kg and diabetes remission in over 40%, self-efficacy in plant-forward healthy eating will mediate its effects on primary biological outcomes, and it will be operationally and financially sustainable.

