**C5g. Physician-Supervised Medication Discontinuation.** Oral hypoglycemic agents (OHA) will be stopped on commencement of TDR, and antihypertensive and diuretic drugs will be stopped or reduced by half (based on physician judgement) on commencement of TDR. OHA, antihypertensive, and diuretic drugs will be reintroduced (as per study protocols) if T2D or hypertension returns. Aspirin will be continued if prescribed because of a previous heart attack or stroke but will be discontinued if prescribed solely because of T2D. Beta-blockers prescribed for the management of angina will be continued. During the PSMD phase, participants will have their blood glucose monitored once a week at the health hub during the Total Diet Replacement and PSMD phase. Participants will also be encouraged to continue recommended monitoring by their primary care providers. For participants in the intensive care group, participants will only have some of their diabetes medications and/or antihypertensive medications discontinued or decreased according to the medication discontinuation protocol. The Medication Discontinuation Protocol gives discretion to the UTHSC Health Hub Medical Director, thus participants in this group will be allowed to continue medications if needed in the estimation of the Medical Director in consultation with their primary care physician. Although PSMD is one of the study procedures, if the Medical Director (in consultation with the primary care provider) decides that a participant needs to continue diabetes and/or antihypertensive medications, they will be allowed to continue them and will not be withdrawn from the study.

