**Table 3: Outcome Measures**

Outcome Measures	Measurement	Schedule
Primary biological outcomes (Aim 2)		
Body weight (kg)	Body weight will be measured without shoes in regular clothes using calibrated scales (Befour Model: WH1061)	Baseline, 3-, 6-, and 12-month visits
		Weekly
Blood pressure (mm Hg)	Systolic and diastolic blood pressure using automated cuffs (Omron Model: HEM-907) using a validated protocol  and number of blood pressure medications by patient report supplemented by medical record review	Baseline, 3-, 6-, and 12-month visits
A1c (%)  and diabetes remission 	Metabolic assessments obtained using standard protocols with diabetes remission defined as A1c < 6.5% after at least 2 months off all antidiabetic medications except GLP-1 agonists and SGLT-2 agonist medications, from baseline, months 6 & 12	Baseline, 6-, and 12-month visits
Secondary metabolic and patient-reported outcomes (Aims 1 and 2)		
Self-efficacy	129,130 Stanford Diabetes Self-Efficacy Scale	Baseline, 6-, and 12-month visits
Diabetes self-management	Two (out of six total) subscales of the revised Summary of Diabetes Self-Care Activities questionnaire for general diet and exercise	Baseline, 6-, and 12-month visits
Secondary sustainability outcomes (Aim 1)		
Program retention (operational sustainability)	Proportion of patients retained in study at each follow-up visit calculated by dividing the number who completed follow-up at each interval by the number expected.	3-, 6-, and 12-month visits
Cost effectiveness of the multicomponent intervention (financial sustainability)	Cost-effectiveness may be calculated using method employed by DiRECT  and recommended by Centers for Disease Control and Prevention.  Incremental total costs per patient related to primary outcomes of body weight (cost per additional kg weight loss), A1c (cost per additional unit A1c reduction), and diabetes remission (cost per additional diabetes remission) at one year calculated using an intention to treat analysis. Effectiveness measured as quality adjusted life years (QALYs) using EQ-5D. 	Following completion of data collection

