**Other Factors.** Covariates will be measured at baseline. These will include demographic characteristics, marital status, education level, insurance, chronic conditions, and SDOH (using electronic health record data collected on all Health Hub clients), and health literacy. At baseline, 6-, and 12-month visits, we will assess prescribed medications. Exposure to each component intervention will be assessed using health coach attendance logs.

**C11. Analysis.** We will evaluate the extent to which the program was implemented according to the protocol, examine if all components of the intervention were delivered in a standardized and reproducible format, and summarize the trial as a flow diagram following Consolidated Standards of Reporting Trials (CONSORT) guidelines. Patient characteristics will be compared between study groups to assess integrity of the random assignment process. Data will be presented as means and standard deviations for continuous variables and as frequencies and percentages for categorical variables. Results will be analyzed based on intention-to-treat.

For Aim 2, we will use baseline, 6-, and 12-month follow-up data to compare differences between treatment and control group means in continuous primary biological outcomes (body weight, blood pressure, and A1c) and secondary patient-reported outcomes (self-care activities related to general diet and exercise). We will use the MIXED procedure of SAS because this is a parallel groups trial with repeated measures assessed over time. In the context of repeated measures ANOVA, we will use t-tests within group to detect change from baseline to 12-months (Follow-up 3) and t-tests between groups to detect the effect of the treatment on the various outcome variables at 12-months. While the preceding hypothesis tests are *a priori* and not adjusted, other comparisons at the intermediary assessments will be adjusted using the Bonferroni method. To examine a difference in the proportion of patients who achieved diabetes remission at 12-month, we will use a chi-square test.

For Aim 1, we will assess intervention operational sustainability as detailed above and in **Table 3**. Based on MODEL study experience providing MI-based HC and TM interventions, we hypothesize that operational sustainability will be high with 12-month program retention rates of approximately 85-90%.

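### The primary blood-pressure outcome is named three ways, and one version, the count of blood-pressure drugs, is changed directly by the protocol in the treatment arm only

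*Combined protocol and SAP*

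**What the plan says.** Four places define or analyse the primary blood-pressure outcome.

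- C1b, Aim 2A: "blood pressure (number of prescribed blood pressure medications".
- C1c: "primary biological outcomes (body weight, number of prescribed blood pressure medications, A1c, and diabetes remission". No measured pressure appears in this list.
- C10, Table 3: the row is labelled "Blood pressure (mm Hg", but its measurement cell holds systolic pressure, diastolic pressure and the "number of blood pressure medications by patient report supplemented by medical record review".
- C11: SAS MIXED is used for "differences between treatment and control group means in continuous primary biological outcomes (body weight, blood pressure, and A1c", with "t-tests between groups to detect the effect of the treatment on the various outcome variables at 12-months". The count is not named. The 12-month tests are declared a priori and left unadjusted.

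What happens to the drugs differs by arm. Under C5g, in the treatment arm "antihypertensive and diuretic drugs will be stopped or reduced by half (based on physician judgement) on commencement of TDR". The PSMD Guidelines say that in general they are stopped on the first day of diet replacement. Elsewhere C5g says that only some drugs are discontinued or decreased, that beta-blockers given for angina stay, that the Medical Director may let a participant continue, and that drugs come back if hypertension returns. In Table 1 the control arm has no study-run discontinuation: the physician is told of the participation and the patient is told to raise medications with the physician. G2 nevertheless describes supervised discontinuation as available to all participants.

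**The concern.** A drug count measures blood-pressure benefit only if the same process decides, in both arms, whether a drug is prescribed. Here the study removes drugs in one arm as part of the package and leaves prescribing in the other arm to usual care. A lower count in the treatment arm may show only that withdrawal was attempted there; a control participant who could equally have done without a drug gets no protocol-driven trial of stopping it.

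The plan calls this a biological outcome, and section D expects the results to bear on whether the programme improves blood pressure. A fall in prescriptions that the protocol produced could then be reported as effectiveness and carried into the design of a larger trial. Because the outcome is not fixed across the four sections, and the 12-month tests are unadjusted, the version reported could also be chosen after the data are seen.

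**Working it through.** **Definitions side by side**

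| Section | Primary blood-pressure outcome | Analysis given |
|---|---|---|
| C1b, Aim 2A | drug count | none |
| C1c | drug count | none |
| C10, Table 3 | mm Hg in the label; systolic, diastolic and count in the cell | none |
| C11 | continuous blood pressure, measure not stated | MIXED, t-test at 12 months |

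No two of the three descriptions (count; mm Hg with count; unspecified continuous) are the same.

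**Inputs from the plan.** C4e: 72 randomized, 15% attrition, about 61 completers. Check: 72 × (1 − 0.15) = 61.2, which reproduces the stated figure, or 30 to 31 per arm. The plan gives no alpha, standard deviation or effect size for blood pressure, so there is no power figure to reproduce.

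**Assumptions (not in the documents).** No true effect on blood pressure; 31 completers per arm; a share p = 50% to 75% on at least one drug; users split 50/35/15% over one, two and three drugs; two-sided 5% t-test on the 12-month count. In the treatment arm a share s of users has all drugs stopped, and a share r of those is back on the original count by month 12.

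**Expected spurious difference.** Mean drugs per user = 0.50×1 + 0.35×2 + 0.15×3 = 1.65. The expected difference in mean count is p × 1.65 × s × (1 − r). For s = 1 and r = 0.6 this is 0.50 × 1.65 × 0.4 = 0.33 to 0.75 × 1.65 × 0.4 = 0.495 drugs per person.

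**Simulated false-positive rate for the count**

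| Users with all drugs stopped (s) | 80% restarted | 60% restarted | 40% restarted |
|---|---|---|---|
| All (worst case) | 10-17% | 30-52% | 61-88% |
| Half | 6-8% | 11-18% | 18-34% |
| A quarter | about 5-6% | 6-8% | 8-12% |

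The ranges run over p; repeat runs move the entries by a point or two. The rate depends on s and r only through s × (1 − r), the share of users still off at month 12. That is why all stopped with 80% restarted (0.20) and half stopped with 60% restarted (0.5 × 0.4 = 0.20) give nearly the same result. If everyone is restarted the rate is the nominal 5%.

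**Second simulation.** With 30 against 31 completers, baseline means of 0.9 to 1.6 drugs and small equal drift in both arms, the 12-month test rejects in 7-9% of trials when 10% of the treatment arm is stopped and not restarted, and in 15-30% when 25% is. On change from baseline the rates are 9-15% and 35-60%. An analysis that uses the baseline count can therefore be more exposed than the first table shows.

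**Measured pressure.** If withdrawn drugs are not all restarted, the treatment arm is compared on less medication than the control arm. This raises its pressure and works against the treatment. C11 does not address one-arm withdrawal for either measure.

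**The case against.** Four points can be made for the plan.

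First, a reader might infer that the arms differ on the count by design. That is secure only just after diet replacement starts. The main test is at 12 months, after a rule to restart drugs when hypertension returns, weekly pressure checks in months 2-4 and periodic checks later. With no blood-pressure effect, many users should be restarted by then, so the count partly reflects whether drugs were needed again. This stands. It makes the bias likely and not certain, because the blood-pressure criterion for restarting is not given in these documents and later monitoring is only described as periodic.

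Second, a halved dose leaves a count unchanged, and C5g allows partial discontinuation and continuation. This also stands. The top row of the table is a worst case, and the lower rows belong beside it.

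Third, a reader might infer that C11 tests a different outcome from Aim 2A. The text does not establish this. C11 says only blood pressure; mm Hg is the natural reading from the Table 3 label, but Aim 2A explains the same term as the count. What can be said is that C11 does not identify the measure and gives no analysis for the count.

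Fourth, medication discontinuation is component 7 of the package, so drug burden is a legitimate outcome of the package. It is, if labelled that way. It does not follow that fewer prescriptions show lower blood pressure, which is how a primary biological outcome would be read.

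**Conclusion.** The concern holds in this form: the primary blood-pressure outcome is inconsistent across Aim 2A, C1c, Table 3 and C11, and the drug count is changed directly by the protocol in one arm, so it cannot serve as clean evidence of improved blood pressure. When some stopped drugs are not restarted, the bias in the count favours the treatment. Its size cannot be fixed from the documents, which give neither the share stopped nor the share restarted. Under the assumptions above, false-positive rates run from near nominal (a quarter stopped, 80% restarted) to 61-88% (all stopped, 40% restarted).

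It would go too far to treat mm Hg as an unbiased replacement, since the same one-arm withdrawal biases it against the treatment. Nor does the defect by itself require systolic pressure alone or rule out any test of the count. The point should be corrected before analysis; it does not undermine the pilot as a whole.

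**What to change.** 1. State the same primary blood-pressure outcome in Aim 2A, C1c, Table 3 and C11: measured pressure in mm Hg, as Table 3 is labelled, at 12 months from the MIXED model.
2. Take the drug count out of the primary biological outcomes. Report it by arm as a medication-use outcome of the whole package (stopped, restarted, continued, never on), and say that it is not evidence of improved blood pressure.
3. State in C11 that the mm Hg result is interpreted with that table, because withdrawal in one arm biases the comparison against the treatment.
4. Reconcile Table 1, C5g, the PSMD Guidelines and G2 on what happens to blood-pressure drugs and in which arm. Which clinical rule is right is for the investigators.

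Cost: wording in these sections. Medications are already assessed at baseline, 6 and 12 months, with record review foreseen in Table 3; stops and restarts between visits would be taken from those records and the discontinuation plans. The sponsor gives up a primary outcome that tends to favour the intervention and accepts a conservative mm Hg comparison.
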